### 8.3 Definitions

#### 8.3.1 Adverse Event

An adverse event (AE) is any untoward medical occurrence in a patient receiving study treatment and which does not necessarily have a causal relationship with this treatment. An AE can be any unfavorable and unintended sign (including an abnormal laboratory finding), symptom, or disease temporally associated with the use of an experimental intervention, whether or not related to the intervention.

- *Diagnostic and therapeutic non-invasive and invasive (i.e., surgical) procedures will not be reported as adverse events. However, the medical condition for which the procedure was performed must be reported if it meets the definition of an adverse event unless it is a pre-existing (prior to protocol treatment) condition.*
- *Abnormal laboratory values or test results constitute adverse events if they induce clinical signs or symptoms or require therapy. They are to be captured under the signs, symptoms or diagnoses associated with them.*

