## 5.2 Toxicities and Dosing Delays/Dose Modifications

Any patient who receives treatment on this protocol will be evaluable for toxicity. Each patient will be assessed for the development of toxicity according to the Time and Events Table (Section 6.4). Toxicity will be assessed according to the NCI Common Terminology Criteria for Adverse Events (CTCAE), version 4.0. Dose adjustments should be made according to the system showing the greatest degree of toxicity.

**Dose modifications** in strength are not permitted for either IL2 or nivolumab.

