**5.2.1.7 Renal:**

Rule out non-inflammatory causes. If non-inflammatory cause, treat accordingly and continue protocol therapy

Grade of elevation in serum creatinine (NCI CTCAE v4)	Management	Follow-up
Grade 1 Serum creatinine >ULN and >baseline but ≤1.5x baseline	
 
Continue nivolumab
 
Monitor serum creatinine weekly
 
	
 
If returns to baseline, resume creatinine monitoring per protocol
 
If worsens, treat as grade 2, 3, or 4
 

Grade 2 or 3 Serum creatinine 1.5x baseline to ≤ 6 x ULN	
 
Delay or discontinue nivolumab
 
Monitor serum creatinine every 2-3 days
 
0.5-1 mg/kg/day methylprednisolone IV or oral equivalent
 
Add prophylactic antibiotics for opportunistic infections
 
Consider renal biopsy
 
	
 
If improves to grade 1                             
 
Taper steroids over at least one month
 
Resume nivolumab and IL-2 if improves to ≤ grade 1 within 12 weeks and corticosteroids have been reduced to ≤ 10 mg oral prednisone or equivalent per day
 
 
 
If elevation persists >7 days or worsens, treat as grade 4
 

Grade 4 Serum creatinine <6x ULN	
 
Discontinue nivolumab
 
Monitor serum creatinine daily
 
1-2mg/kg/day methylprednisolone IV or IV equivalent
 
Add prophylactic antibiotics for opportunistic infections
 
Consult nephrology
 
Consider renal biopsy
 
	
 
If improves to grade 1                             
 
Taper steroids over at least one month
 
Resume nivolumab and IL-2 if improves to ≤ grade 1 within 12 weeks and corticosteroids have been reduced to ≤ 10 mg oral prednisone or equivalent per day
 
 
 

**For nivolumab only** with any grade 4 **hematologic toxicity**, hold nivolumab. If the adverse event improves to grade 3 or better with symptomatic management and/or supportive medications, nivolumab may be resumed in ≥2 weeks.

Discontinue both IL-2 and Nivolumab permanently for the following conditions:

- Guillain-Barre Syndrome (GBS)
- Myasthenia gravis
- Pituitary apoplexy or hypopituitarism (clinical including based on biochemical values).

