### 8.2 Adverse Event Reporting Requirements

Adverse event (AE) monitoring and reporting is a routine part of every clinical trial and is done to ensure the safety of subjects enrolled in the studies as well as those who will enroll in future studies using similar agents. Data on adverse events will be collected from the time of initial study treatment administration or intervention through 60 days after the last dose of **study treatment** (study treatment here refers to the two possible cycles of interleukin-2 and/or last dose of nivolumab up to 48 weeks of therapy, whichever is later). Any serious adverse event that occurs more than 60 days after the last study treatment and is considered related to the study treatment must also be reported. Serious Adverse Events (SAEs) will continue to be followed until:

- Resolution or the symptoms or signs that constitute the serious adverse event return to baseline;
- There is satisfactory explanation other than the study treatment or intervention for the changes observed; or
- Death.

The investigator is responsible for the detection, documentation, grading and assignment of attribution of events meeting the criteria and definition of an AE or SAE. The definitions of AEs and SAEs are given below. It is the responsibility of the principal investigator to ensure that all staff involved in the trial is familiar with the content of this section.

Any medical condition or laboratory abnormality with an onset date before initial study treatment administration or intervention is considered to be pre-existing in nature. Any known pre-existing conditions that are ongoing at time of study entry should be considered medical history.

All events meeting the criteria and definition of an AE or SAE, as defined in Section 8.3, occurring from the initial study treatment administration or intervention through 60 days following the last dose of the study treatment (study treatment here refers to the two possible cycles of interleukin-2 and/or last dose of nivolumab up to 48 weeks of therapy whichever is later) or study intervention must be recorded as an adverse event in the patient's source documents and on the CRF regardless of frequency, severity (grade) or assessed relationship to the study treatment or intervention.

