## 11.2 Data Analyses Plans

Primary Endpoint Analysis:

Phase 1b: DLT count and proportion will be reported. Type, grade and attribution will be described by body system in the first 10 DLT evaluable patients. Number of IL-2 cycles and doses and Nivolumab doses will be summarized.

Phase II: Overall response rate at 12 weeks will be reported with the sample size and proportion of evaluable patients and the corresponding 95% exact binomial confidence interval.

Secondary Endpoint Analyses:

Safety will be defined by frequency of drug-related grade 3-5 adverse events including adverse events of interest within the duration of protocol, specified therapy and an additional 60 days following the last dose with the combination of HD IL2 and nivolumab, as assessed by NCI's CTCAE version 4.0. Counts and frequencies will be reported by body system, type and grade. Cycles and of each drug and doses/cycle of IL-2 will be described using descriptive statistics.

Survival endpoints are 24-month Overall Survival (OS) and 24-month Progression-Free Survival (PFS) as assessed by RECIST 1.1 criteria in subjects treated with the combination. Product-limit estimates from Kaplan-Meier methods will be used to report the 24-month OS and PFS proportions with 95% confidence intervals. Kaplan-Meier figures will be produced.

Interim Analysis for efficacy: An interim analysis for efficacy is planned after 12 response evaluable patients have been enrolled (total in the phase I b/II portions). If 2 or less patients have a response at 12 weeks then the trial will terminate. .

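### Section 8.3.1 sets no grade trigger for laboratory adverse events, so some asymptomatic, untreated grade 3-4 laboratory toxicity can be missing from the secondary safety endpoint

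*Combined protocol and SAP*

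**What the plan says.** Section 8.3.1 first defines an adverse event broadly: "An AE can be any unfavorable and unintended sign (including an abnormal laboratory finding), symptom, or disease". A bullet beneath it then sets a condition for laboratory results: "Abnormal laboratory values or test results constitute adverse events if they induce clinical signs or symptoms or require therapy". On how to record those that qualify, it adds: "They are to be captured under the signs, symptoms or diagnoses associated with them".

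Section 8.2 ties CRF recording to that definition. What must be entered is "All events meeting the criteria and definition of an AE or SAE, as defined in Section 8.3", from first treatment to 60 days after the last dose.

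Section 11.2 gives the phase II secondary safety analysis: "Safety will be defined by frequency of drug-related grade 3-5 adverse events including adverse events of interest". Counts are to be reported by body system, type and grade. The Study Endpoints part of section 2.0 defines the endpoint in similar terms. Section 7.2 analyses safety in everyone who received at least one dose.

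Section 5.2 grades toxicity with no symptom or treatment condition: "Toxicity will be assessed according to the NCI Common Terminology Criteria for Adverse Events (CTCAE), version 4.0".

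**The concern.** The endpoint presents itself as a CTCAE grade 3-5 frequency. Many CTCAE laboratory grades depend on the number alone, but entry to the endpoint depends on symptoms or treatment. A value can be grade 3 or 4, lead to a delay or hold of study drug, recover without treatment, and never become a recordable event.

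The error runs in one direction: it can only lower the reported grade 3-5 frequency. Safety of the combination is a named phase II secondary objective, and the synopsis gives the two monotherapies as the reference. The nivolumab reference table reproduced in sections 1.2 and 9.2 includes laboratory-type terms such as anemia, hyperglycemia and hypertriglyceridemia. Counting such findings by a narrower rule here would flatter the combination.

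The documents also do not say whether holding a drug counts as therapy. Each of the 4 sites would have to decide that for itself.

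**Working it through.** The plan states no figure on this point, so there is nothing to reproduce. The check compares the sections and then gives a bounded illustration.

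**1. Does the bullet gate the endpoint?** 8.3.1 sets the condition, 8.2 requires recording only of what meets 8.3, and 11.2 counts adverse events. The bullet says if rather than only if. But the general sentence above it already admits any abnormal laboratory finding, so the bullet does nothing unless it restricts.

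**2. Which asymptomatic grade 3-4 findings pass?**

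| Finding | Position under 5.2.1 and 11.1 | In the endpoint? |
|---|---|---|
| Immune-mediated hepatic, after nivolumab | 5.2.1.4: defined by AST/ALT or bilirubin alone; corticosteroid listed | Yes |
| Immune-mediated renal, after nivolumab | 5.2.1.7: defined by creatinine alone; corticosteroid listed | Yes |
| Blood count | No table; grade 4 leads to a nivolumab hold, grade 3 has no rule of its own there | Not if untreated |
| Liver or creatinine change in an IL-2 cycle before nivolumab | 5.2.1 applies only once a nivolumab dose has been given | Not if untreated |
| Reversible IL-2 change | 11.1 excludes it from events of interest | Not if untreated |
| Change judged non-inflammatory | Leaves the path of the 5.2.1 tables | Not if no treatment is needed |

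The first two rows pass for two reasons. The listed corticosteroid meets the therapy condition, and 11.2 names events of interest as part of the endpoint. The pre-nivolumab row applies to both IL-2 cycles in the first 3 patients, whose treatment is sequential (5.1.4).

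**3. Is the bullet consistent with the rest of the plan?** No. It conflicts with the general sentence of 8.3.1 and with the unconditional CTCAE grading in 5.2. The hematologic rule printed below the renal table in 5.2.1.7 reads: "If the adverse event improves to grade 3 or better with symptomatic management and/or supportive medications, nivolumab may be resumed". There a grade 4 blood count is called an adverse event. Under 8.3.1 it would not be one if it recovered on the hold alone, without symptoms or treatment.

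**4. Can an unrecorded value affect treatment?** Yes. Under 5.2, IL-2 toxicity above grade 1 (fatigue has its own limit) holds nivolumab and the second IL-2 cycle. A delay of more than 6 weeks ends study therapy, with an exception for steroid tapers. An asymptomatic laboratory toxicity could act through this rule without being a recordable adverse event.

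**5. Is the DLT count affected?** No. Section 11.1 defines a DLT as a grade 3 or 4 immune-mediated event of interest under 5.2.1. It does not refer to the laboratory bullet.

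**6. Size.** The documents do not say how often such values occur. Assume the trial runs to full size, with 23 (evaluable) to 28 (maximum registered) treated patients. In an any-event proportion, each patient whose only drug-related grade 3-5 event is an uncounted laboratory value then costs

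- 1/28 = 3.6 points, to
- 1/23 = 4.3 points.

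An illustration with assumed inputs: if 16/23 = 69.6% truly had an event, losing 2 gives 14/23 = 60.9%, and losing 5 gives 11/23 = 47.8%. Neither the 16 nor the 2 and 5 come from the documents. In the tabulation by type and grade that 11.2 specifies, an uncounted event is lost from its own row even if the patient has another grade 3-5 event.

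**The case against.** Four points can fairly be made for the plan.

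- **A symptom-or-therapy threshold is a deliberate reporting choice, and the wording is ambiguous rather than exclusionary.** 8.2 also makes worsening of a pre-existing condition an adverse event, and the hematologic rule treats a grade 4 count as one. This stands in part: the text conflicts with itself more than it states a clean exclusion. But a site that follows the bullet literally will leave new-onset values out.
- **Hepatic and renal toxicity is largely protected.** A reader might infer that all asymptomatic grade 3-4 liver and kidney toxicity drops out. The documents do not support that: the immune-mediated events after nivolumab are defined by laboratory value, have treatment listed, and are named in the endpoint.
- **No decision rule depends on the bullet.** A reader might infer that one uncounted laboratory event could turn 6 DLTs in 10 into 5, and so a pause into a continuation. Section 11.1 ties DLTs to 5.2.1, so this does not follow. Whether an event is immune mediated is a question of attribution, which 8.3.1 does not govern.
- **The data are not lost.** CBC and chemistry are scheduled at IL-2 weeks, nivolumab visits and end of treatment (6.2, 6.4), and section 15.0 requires all data to be entered. This stands in full. The gap is in what is counted as an adverse event, which is why it is cheap to close.

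**Conclusion.** The point holds in a limited form. The bullet in 8.3.1, acting through 8.2, lets asymptomatic, untreated grade 3-4 laboratory toxicity outside the 5.2.1 steroid tables go missing from the secondary endpoint of drug-related grade 3-5 adverse events. The clearest case is a grade 4 blood count that holds nivolumab and recovers without treatment. The bias is downward.

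This rests on reading the bullet as a restriction and on a dose hold not counting as therapy. The first is the only reading that gives the bullet a function; on the second the documents are silent.

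No total can be given for the undercount. The cost of 3.6 to 4.3 points per patient applies only to an any-event proportion, which 11.2 does not specify, and only to patients with no other drug-related grade 3-5 event. Section 1.2 describes IL-2 toxicity in many organ systems, so the documents give no basis for saying how many such patients there would be. The phase Ib DLT rule and the response endpoint are untouched. The change should be made, but it does not threaten the design.

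**What to change.** Amend 8.3.1 so that two kinds of laboratory value are recorded as adverse events under their CTCAE term, whether or not they cause symptoms or need therapy:

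- any treatment-emergent value of CTCAE grade 3 or higher;
- any value, of whatever grade, that leads to a delay, hold or stop of IL-2 or nivolumab.

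Keep the present rule for all other grade 1-2 values. This removes the conflict with the general sentence of 8.3.1 and with 5.2, and it makes the question of whether a hold is therapy irrelevant. It changes recording only, not patient management.

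Alternatively, leave 8.3.1 alone and add to 11.2 a table of worst on-treatment CTCAE laboratory grade, from the scheduled CBC and chemistry results, for all patients who received at least one dose. This is lighter on sites. It leaves the contradiction in place, however, and shows the missing events beside the adverse event endpoint rather than within it.

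The cost of the amendment is one sentence, more adverse event entries and attribution calls (possibly many, since laboratory changes may be frequent with IL-2), and a less favourable reported grade 3-5 frequency. No new tests are needed.

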#### 8.3.2 Serious Adverse Event

An adverse event is considered “serious” if, in the view of either the investigator or Sponsor-Investigator, it results in any of the following outcomes:

- Death  
If death results from (progression of) the disease, the disease should be reported as event (SAE) itself.
- A life-threatening adverse event  
An adverse even is considered ‘life-threatening’ if, in the view of either the investigator [or sponsor], its occurrence places the patient or subject at immediate risk of death. It does not include an adverse event that, had it occurred in a more severe form, might have caused death.
- Inpatient hospitalization or prolongation of existing hospitalization for  $\geq 24$  hours.
- A persistent or significant incapacity or substantial disruption of the ability to conduct normal life functions
- A congenital anomaly/birth defect
- Important medical event  
Any event that may not result in death, be life-threatening, or require hospitalization may be considered serious when, based upon appropriate medical judgment, they may jeopardize the patient and may require medical or surgical intervention to prevent one of the outcomes listed in this definition of “Serious Adverse Event”. Examples of such medical events include allergic bronchospasm requiring intensive treatment in an emergency room or at home; convulsions that do not result in inpatient hospitalization or the development of drug dependency or drug abuse.

Previously planned (prior to signing the informed consent form) surgeries should not be reported as SAEs unless the underlying medical condition has worsened during the course of the study.

Preplanned hospitalizations or procedures for preexisting conditions that are already recorded in the patient's medical history at the time of study enrollment should not be considered SAEs.

**Hospitalization or prolongation of hospitalization without a precipitating clinical AE (for example, for the administration of study therapy (e.g. HD IL2) or other protocol-required procedure) should not be considered SAEs.** However, if the preexisting condition worsened during the course of the study, it should be reported as an SAE.

### 8.3.3 Expected Adverse Events

An adverse event (AE) is considered "expected" if:

- For approved and marketed drugs or devices, those adverse events are described in the approved Package Insert (Label).
- For investigational new drugs or devices, those adverse events are described in the FDA Investigator's Brochure.
- In clinical research studies, information on expected adverse events is also summarized in the protocol and in the consent document. See section 9.1 for the list of expected adverse events related to the drug under study.

### 8.3.4 Unexpected Adverse Event

An adverse event (AE) is considered "unexpected" if it is not described in the Package Insert, Investigator's Brochure, in published medical literature, in the protocol, or in the informed consent document.

## 8.4 Adverse Event Characteristics

### 8.4.1 CTCAE Term

(AE description) and grade: The descriptions and grading scales found in the NCI Common Terminology Criteria for Adverse Events (CTCAE) version 4.0 will be utilized for AE reporting. All appropriate treatment areas should have access to a copy of the CTCAE version 4.0. A copy of the CTCAE version 4.0 can be downloaded from the CTEP web site. (<http://ctep.cancer.gov>)

### 8.4.2 Attribution of the AE

The investigator or co-investigator is responsible for assignment of attribution.

Definite – The AE *is clearly related* to the study treatment/intervention.

Probable – The AE *is likely related* to the study treatment/intervention.

Possible – The AE *may be related* to the study treatment/intervention.

Unlikely – The AE *is doubtfully related* to the study treatment/intervention.

Unrelated – The AE *is clearly NOT related* to the study treatment/intervention.

## 8.5 Serious Adverse Event Reporting Guidelines

- 8.5.1** The Sponsor-Investigator and Coordinating Center must be notified within **24 hours** of study team's knowledge of all events meeting the criteria and definition of a serious adverse event that are unexpected and possibly related (definite, probable or possible) to study treatment administration, occurring during the study or within 60 days of the last administration of the study treatment. All other SAEs not meeting the criteria of unexpected and possibly related should be reporting to the Sponsor-Investigator and Coordinating Center within 5 business

days of study team's knowledge. All SAEs should be reported using the CTO SAE Form.

**8.5.2** The investigator must report all events meeting the criteria and definition of a serious adverse event that are unexpected and possibly related (definite, probable or possible) to study treatment administration or intervention to the local IRB within 5 business days of study team's knowledge if death or life threatening, and within 7 calendar days for all others or per local institutional guidelines.

**8.5.3** A copy of the CTO SAE form as available in the study database should be sent to the Sponsor-Investigator (see below for contact info) and also to the Coordinating Center via email to [[contact]](mailto:[contact]).

Contact information for the PI for notification of SAEs:

[name], MS  
[name],  
University of Michigan,  
[name]  
[name]

Ph: [contact]  
[contact]  
Email: [[contact]](mailto:[contact])

Follow-up information must also be reported within 7 business day of the site's knowledge of the information.

**8.5.4** The Coordinating Center will disseminate information regarding SAEs to the participating sites within 5 days of review of the information by the Sponsor-Investigator (or designee in the event of extended absence) only in the case that the event(s) is believed to be related (i.e., possibly, probably, or definitely) to the study treatment. The Coordinating Center will be responsible for reporting of events to supporters, as appropriate (outlined below). The Michigan Institute for Clinical and Health Research (MICHR) MIAP group will be responsible for reporting any SAEs to the FDA as outlined below.

**8.5.5** In this trial, serious unexpected adverse events believed to be definitely, probably or possibly related to the study treatment will be reported to the Food and Drug Administration via the MedWatch 3500A according to the reporting requirements in 21 CFR 312.32. The MICHR MIAP group, in cooperation with the Coordinating Center, will be responsible for correspondence regarding adverse events with the FDA for all participating sites.

**8.6 Routine Reporting**

All other adverse events- such as those that are expected, or are unlikely or definitely not related to the study participation- are to be reported annually as part of regular data submission.

**8.7 Reporting of Unanticipated Problems**

There are types of incidents, experiences and outcomes that occur during the conduct of human subjects' research that represent unanticipated problems but are not considered adverse events. For example, some unanticipated problems involve social or economic harm instead of the physical or psychological harm associated with adverse events. In other cases, unanticipated problems place subjects or others at increased risk of harm, but no harm occurs.

Upon becoming aware of any incident, experience, or outcome (not related to an adverse event) that may represent an unanticipated problem, the investigator should assess whether the incident, experience, or outcome represents an unanticipated problem. The incident, experience or outcomes is considered unanticipated if it meets all of the following criteria:

1. Unexpected (in terms of nature, severity, or frequency);
2. Related or possibly related to participation in the research; and
3. Suggests that the research places subjects or others at a greater risk of harm than was previously known or recognized.

If the investigator determines that the incident, experience, or outcome represents an unanticipated problem, the investigator must report it to the IRB within 14 calendar days of the study team becoming aware of the problem.

